## **11. STATISTICAL METHODS**

### **11.1. Primary endpoints**

- Occurrence of adverse events (AEs) from first vaccination (Day 1) up to Day 61.
  - Occurrence of each solicited local and general AE, during a 7-day follow-up period after each vaccination (i.e., the day of vaccination and 6 subsequent days).
  - Occurrence of any unsolicited AE, during a 30-day follow-up period after each vaccination (i.e., the day of vaccination and 29 subsequent days).
  - Occurrence of any serious adverse event (SAE) from Day 1 up to Day 61.
  - Occurrence of episode of spontaneous or excessive bleeding (AE of special interest), during a 30-day follow-up period after each vaccination.

## 11.2. Secondary endpoints

- Occurrence of RSV-RTI, RSV-LRTI, severe RSV-LRTI and very severe RSV-LRTI (according to standardized case definitions) as from first vaccination (Day 1) up to the end of the first RSV transmission season.
- Occurrence of RSV-RTI, RSV-LRTI, severe RSV-LRTI and very severe RSV-LRTI (according to standardized case definitions) as from first vaccination (Day 1) up to the end of the second RSV transmission season.
- Occurrence of SAEs from first vaccination (Day 1) up to the end of the second RSV transmission season.
- Occurrence of RSV-LRTI (AE of special interest) as from first vaccination (Day 1) up to the end of the first RSV transmission season, and up to the end of the second RSV transmission season.
- Occurrence of very severe RSV-LRTI (according to standardized case definitions) among RSV infected infants with a negative RSV exposure status (at screening based on in-stream baseline serological testing) from first vaccination (Day 1) up to the end of the first RSV transmission season.
- Humoral response to the investigational RSV vaccine, pre-vaccination (Screening), post-Dose 1 (Day 31) and post-Dose 2 (Day 61 and at the end of the first RSV transmission season):
  - Neutralizing antibody titers against RSV-A.
  - RSV F antibody concentrations.

## 11.3. Tertiary endpoints

- Humoral response to the investigational RSV vaccine, pre-vaccination (Screening), post-Dose 1 (Day 31) and post-Dose 2 (Day 61).
  - *Palivizumab*-competing antibody concentrations.
- Any further exploratory immunology to detect disease-related or vaccine-related immune responses, such as but not limited to:
  - Anti-vector immunity: neutralization.

## 11.4. Determination of sample size

The sample size determination is based on the minimum number of subjects needed to allow detection of a serious ERD signal having a magnitude similar to that of the historic FI-RSV vaccine trials [Kim, 1969]. A total of 150 infants will be enrolled and randomized with 1:1:1 ratio to receive either 1 dose of the  $1.5 \times 10^{10}$  vp/dose ChAd-155 RSV vaccine [the 1D RSV + comparator group], 2 doses of the  $5 \times 10^{10}$  vp/dose ChAd-155 RSV vaccine [the 2D RSV + comparator group], or no ChAd-155 RSV vaccine [the comparator/Placebo control alone group].

[figure not shown]
An effect of vaccination on ERD will be monitored very closely. It is anticipated that at least 50% of subjects [Dunn, 2013] will have a negative RSV exposure status (at screening which will be assessed by in-stream serological testing of baseline samples). While the rate of RSV infection could be highly variable by season, a conservative rate of infection of 20% in the first season is assumed [Kutsaya, 2016]. Therefore, with 50 infants in each RSV vaccine group, it is anticipated to observe at least 5 infected infants with a negative RSV exposure status (at screening based on in-stream baseline serological testing) in each RSV vaccine group [ $50 \times 0.5 \times 0.2 = 5$ ].

With a one-sided type I error of 0.05, and the assumption of a 10% rate of infection progressing to very severe RSV-LRTI (which is a conservative assumption based on the rate in the natural history of disease), 5 infections can provide at least 90% statistical power to demonstrate the progression rate from infection to very severe RSV-LRTI is less than 80%. That is less extreme than that observed in the historic FI-RSV vaccine trial where 80% of RSV RTI cases progressed to hospitalization [Kim, 1969]. During the course of the study, since the actual negative RSV exposure status (at screening based on in-stream baseline serological testing) and infection rates may be lower than 50% and 20%, respectively, the sample size **may** be adjusted as needed through additional recruitment in order to achieve **a sufficient number of** RSV infected infants with a negative RSV exposure status (at screening based on in-stream baseline serological testing) in each RSV vaccine group (**Amended 1 August 2019**).

If a maximum of 1 out of 5 infections in infants receiving ChAd-155 RSV vaccine progress to very severe RSV-LRTI, then it can be concluded with 95% confidence that the expected progression rate of infection is less than the effect reported in previous FI-RSV trials; if a minimum of 3 out of 5 infections progress to very severe RSV-LRTI then it can be concluded with 95% confidence that the expected progression rate of infection is more than the 10% observed in natural history of infection. The above power analysis is based on the procedure of inequality of one proportion in PASS 12.

With 50 subjects in each RSV vaccine group, the probability of observing at least one SAE would be about 92% if the true incidence rate of SAE is 5%. For estimating the proportion of subjects with AEs, the maximum width of exact 95% confidence interval (CI) would be under 30%, and it could be as large as 35% if attrition rate is 30%.

**Figure 6** illustrates the precision on the estimate for the proportion of subjects with AEs following vaccination with each RSV formulation based on the number of subjects with AEs observed from 50 subjects.

**Figure 6    Exact 95% confidence interval on the proportion of subjects with adverse events following vaccination based on 50 enrolled subjects**

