### 11.12.1. Sequence of analyses

In preparation of the planned iSRC and IDMC evaluations, analyses of all available safety data (i.e., data that are as clean as possible) will be performed (see Section 9.10 for more information). These analyses will be done by an *independent data analysis center* to maintain the blinding of the study, and will be documented in a statistical analysis report. Only the outcome of the iSRC and IDMC reviews will be communicated to the RSV study team (no safety signal or safety signal). No clinical study report will be written (**Amended 1 August 2019**).

The statistical analyses will be performed in 3 steps:

- An analysis will be performed when all data up to Day 61 are available. Additional safety data available at the time of this analysis will be described. At this point, the statistician will be unblinded (i.e., individual subject treatment assignments will be available) and the study will be conducted in a single blind manner, with patients remaining blinded up to the last study visit (end of the second RSV transmission season). Summary results may unblind some specific subjects but no individual listings will be provided and the investigator will not have access to the treatment allocation up to the last study visit (end of the second RSV transmission season), except in case of emergency unblinding (see Section 9.8).
- An analysis will be performed when all data up to Visit 7 (end of the first RSV transmission season) are available. No individual listings will be provided.
- The final analysis will be performed when all data up to study conclusion (end of the second RSV transmission season) are available. An integrated clinical study report containing all data will be written and made available to the investigators at that time.

If the data for tertiary endpoints become available at a later stage, (an) additional analysis/ analyses will be performed. These data will be documented in annex(es) to the study report and will be made available to the investigators at that time.

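### Section 11.4 presents 5 exposure-negative infections per RSV vaccine group as a minimum, but 5 is the mean: the chance of reaching it is 57% per group and 32% in both groups

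*Protocol*

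**What the plan says.** Section 11.4 sizes the trial on progression from RSV infection to very severe RSV-LRTI in infants with a negative RSV exposure status. It reasons that "with 50 infants in each RSV vaccine group", "it is anticipated to observe at least 5 infected infants with a negative RSV exposure status" in each RSV vaccine group, and shows the product 50 x 0.5 x 0.2 = 5. The power statement follows: "With a one-sided type I error of 0.05" and "the assumption of a 10% rate of infection progressing to very severe RSV-LRTI", "5 infections can provide at least 90% statistical power to demonstrate the progression rate from infection to very severe RSV-LRTI is less than 80"%.

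The section treats 50% exposure-negative as a lower figure and 20% infected as conservative. It also concedes that the actual exposure-negative share and "infection rates may be lower than 50% and 20%, respectively". In that event Sections 5.1 and 11.4 allow, but do not require, more recruitment to reach a sufficient number of such infections. Neither section gives the number.

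Two other places matter. Section 9.10.3 makes an additional progression analysis for the IDMC depend on at least 5 exposure-negative infections in every randomized group, control included. Section 11.11 concludes that the rate is below that of the historic FI-RSV trials if the one-sided 95% upper bound is under 80%. It sets no minimum number of infections.

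**The concern.** A product of planning rates gives a mean, and a mean of 5 is missed in a large share of trials. Section 11.4 uses it as if it were assured, then attaches power to exactly that count. Section 1.2.1 describes the comparison of regimens as powered to exclude FI-RSV-level risk, so a reader will take the 90% as a property of the 150 enrolled infants. It is a property of 5 infections. The same figure of 5 acts as a gate in 9.10.3, so overstating how likely it is also overstates how likely the IDMC is to receive that analysis. The recruitment option that could make up a shortfall has no target.

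**Working it through.** **Inputs (Section 11.4).** N = 50 infants per RSV vaccine group; exposure-negative share 0.5; first-season infection rate 0.2; null progression rate 0.80; assumed true rate 0.10; one-sided alpha 0.05.

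**1. The plan's own figures.** Expected infections: 50 x 0.5 x 0.2 = 5. Exact binomial test with 5 infections, success if at most 1 progresses:
- Type I error: P(X <= 1 | n = 5, p = 0.8) = 0.0067. Allowing 2 would give 0.0579, above 0.05, so the rule of at most 1 of 5 is right.
- Power: P(X <= 1 | n = 5, p = 0.1) = 0.9^5 + 5 x 0.1 x 0.9^4 = 0.5905 + 0.3281 = 0.919.

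Both stated figures reproduce.

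**2. Chance of reaching 5.** Each enrolled infant is an exposure-negative infection with probability 0.5 x 0.2 = 0.10, so the count is Binomial(50, 0.10). With P(n) = C(50, n) x 0.1^n x 0.9^(50-n), the probabilities for n = 0 to 4 are 0.0052, 0.0286, 0.0779, 0.1386 and 0.1809, which sum to 0.431.
- One RSV group: 1 - 0.431 = 0.569.
- Both RSV groups: 0.569^2 = 0.324.
- All three randomized groups (condition in 9.10.3, same rates in control): 0.569^3 = 0.184.

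Fixing exactly 25 exposure-negative infants per group hardly changes this: 57.9% and 33.6%.

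**3. Power over the random count.** The exact critical value is recalculated for each n (largest c with P(X <= c | n, 0.8) <= 0.05):

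| Infections n | Success if X <= | Type I error | Power at 10% |
|---|---|---|---|
| 0 or 1 | not possible | – | 0 |
| 2 | 0 | 0.040 | 0.810 |
| 3 | 0 | 0.008 | 0.729 |
| 4 | 1 | 0.027 | 0.948 |
| 5 | 1 | 0.007 | 0.919 |
| 6 | 2 | 0.017 | 0.984 |
| 7 | 3 | 0.033 | 0.997 |

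Weighting by P(n):
- n = 2, 3, 4: 0.0779 x 0.810 + 0.1386 x 0.729 + 0.1809 x 0.948 = 0.063 + 0.101 + 0.171 = 0.336 (from unrounded terms).
- n of 5 or more: 0.551.
- Total: 0.886 per group. Both regimens succeeding: 0.886^2 = 0.785.

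**4. Other rates (assumed, not in the protocol as a range).**

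| Exposure-negative | Infected | P(5 or more), one group | Unconditional power, one group |
|---|---|---|---|
| 50% | 10% | 10% | 60% |
| 50% | 20% | 57% | 89% |
| 60% | 20% | 73% | 93% |
| 50% | 30% | 89% | 97% |

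**The case against.** The power sentence is explicitly about 5 infections, and it is true. Falling short of 5 is not failure: 4 infections give 94.8% power and 2 give 81.0%. The inputs are also presented as cautious, and Section 1.1.1 cites 50–70% of infants infected in the first year of life. All of this stands. It limits the consequence for power to a small one, but it does not turn a mean into a minimum. Even at an assumed 60% exposure-negative, the chance of 5 or more is 73% per group, and Section 11.4 itself allows that the rates may be lower.

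Several stronger readings are tempting, but the documents do not support them.

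- **That the 90% power is simply not delivered, or is really 55%.** The 0.551 in the working becomes the power only if fewer than 5 infections counts as failure. The protocol sets no such rule for its Visit 7 or final analysis; the minimum of 5 applies only to the additional IDMC analysis.
- **That 79% is a missed target.** Nothing requires both regimens to succeed.
- **That 30% attrition should be applied.** With 35 infants the chance of 5 or more would be 27% and the power 76%. But Section 11.4 raises 30% only as a hypothetical for adverse-event precision. Section 10.2.1 keeps data up to withdrawal, and Section 11.5 analyses all vaccinated infants.
- **That the study team cannot operate the recruitment option.** Section 11.12.1 does say "Only the outcome of the iSRC and IDMC reviews will be communicated to the RSV study team (no safety signal or safety signal"), but the same section unblinds the statistician at the Day 61 analysis. Section 9.10.3 already has the independent data analysis center work with a by-group count of 5.
- **That passing on 0 of 2 infections is an error.** It is a valid exact result with type I error 0.04.

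**Conclusion.** The point holds as a misstatement of a planning figure on which the sample size rests. At the protocol's own values, 5 or more exposure-negative infections occur with probability 57% in one RSV group, 32% in both and about 18% in all three randomized groups. At the planned size, the analysis in 9.10.3 would therefore more likely than not go untriggered. The conditional power is right at 91.9%. Unconditionally it is about 89% per group, 1.4 points under 90%.

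These figures assume that infants are independent at fixed rates, that the groups are independent, and, for the 18%, that control has the same rates as the vaccine groups. A shared good or bad season would make the groups' counts move together, so the joint figures are specific to fixed rates. The endpoint is secondary, but it is the stated basis of the sample size.

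**What to change.** In Section 11.4:
- Replace 'at least 5' by '5 expected (57% chance of 5 or more per group, 32% in both RSV groups)'.
- Say that the 90% power is conditional on 5 infections.
- Give the unconditional power of about 89% per group, with a range for other rates, labelled as assumed: for example 93% at 60% exposure-negative and 20% infected, and 60% at 50% exposure-negative and 10% infected.

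In Sections 5.1 and 11.4, replace the unquantified sufficient number by 5, the figure that the power statement and 9.10.3 already use. State that the independent data analysis center applies the count by group.

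This is a text change. The stated figures become somewhat less favourable, and the restatement itself requires no extra enrolment. If the sponsor later uses the recruitment option to reach 5, that means more infants, as the current text already allows. For scale, at the planning rates a 90% chance of 5 or more would need 78 infants per group for one group, or 89 per group for both RSV groups.

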### 1.2.2.2. Choice of study population

Infants aged 6 and 7 months were selected to be vaccinated in this study because:

- Infants of this age are more likely to be unexposed to RSV compared to older infants [Dunn, 2013].
- The natural course of RSV disease is generally less severe at this age. Their airways are relatively larger and they are therefore less at risk of serious RSV-RTI than younger infants.
- Risk of adverse outcome of natural infection following FI-RSV vaccination was more pronounced when the vaccine was administered to younger infants.

For safety reasons, the population will have no predisposing risk factors for severe outcome following RSV disease (e.g., premature birth, past or current chronic lung disease, or cardiovascular disease).

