All subjects with symptoms of RTI detected by active or passive surveillance contacts will be reviewed by the investigator as soon as possible and those based on any suspicion of difficulty in breathing, wheezing or parental concern seen within 24 hours (refer to Section 9.2). This will ensure prompt assessment of need for medical care.

All cases of RSV-LRTI will be considered as adverse events (AEs) of special interest (refer to Section 9.1.5) and will have to be reported within 24 hours to the sponsor, and notified to the IDMC (which is not blinded), together with full case details, within 48 hours upon sponsor becoming aware. In order to support this timely reporting, the investigator will make the diagnosis according to his/her medical judgment and locally-available diagnostic tests of RSV infections. Criteria for hospitalization are not protocol defined but based on the attending clinicians' judgment of medical need.

The IDMC will receive on a regular basis cumulative summary reports of the number of RSV infections (asymptomatic and symptomatic) and the proportion progressing to hospitalization in the vaccinees by group and the incidence of RSV-RTI, RSV-LRTI and severe RSV-LRTI according to standardized case definitions by group (refer to Section 4.1). The frequency will be initially monthly from the beginning of the RSV season and will be adapted based on the instruction of the IDMC (refer to Section 9.10.3). The objective of this intense monitoring of cumulative RSV-RTI data by the IDMC is to ensure that, if it occurs, ERD is detected early in the course of the study allowing enrolment to be stopped and thereby minimizing the number of infants exposed to the ChAd155-RSV vaccine.

The final analysis of the incidence of RSV-LRTI by group will be performed according to the standardized case definitions for clinical symptomatology and diagnostic test at sponsor's laboratory (refer to Table 6) ensuring consistency across sites.

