### **11.10. Analysis of RTI and LRTI**

The primary analysis will be performed on the ES of subjects with a negative RSV exposure status (at screening based on in-stream baseline serological testing) in the pooled single dose RSV vaccine group, the pooled two dose RSV vaccine group, and the pooled comparator group separately for first and second RSV seasons and overall. A similar analysis will be performed on the entire ES. As primary analysis, the assessment of RSV infection will be performed using the quantitative RT-PCR according to standardized case definitions (see [Table 6](#)) based on the available WHO case definitions.

The number of RSV infections within each group and the maximum disease severity of the event will be tabulated. The rate (with 95% CI) of RSV-RTI and RSV-LRTI and infections progressing to hospitalization will be evaluated for each of the three pooled groups.

The ***incidence*** rate of very severe RSV-LRTI among RSV infected infants with a negative RSV exposure status (at screening based on in-stream baseline serological testing) from first vaccination (Day 1) up to the end of the first RSV transmission season will be estimated as well as 95% one-sided lower CI.

The **incidence rate** and the relative risk of subjects with RSV-associated RTI (with 95% CI) between each of two pooled RSV vaccine groups and the pooled control group will be calculated for both the cohort of subjects with a negative RSV exposure status (at screening based on in-stream baseline serological testing) on the ES and on the entire ES. The same descriptive analysis will be performed for RSV-associated LRTI and RSV-associated severe LRTI (**Amended 1 August 2019**).

Descriptive analyses (mean, median, min, max) of viral load assessed by the quantitative RT-PCR (RSV-A/B) of all cases as listed in [Table 6](#) will be tabulated by case category. This analysis will also be done on the three pooled groups.

The incidence rate of all cases as listed in [Table 6](#) (with 95% CI) will be calculated by the three pooled groups. The same descriptive analysis will be performed for all cause LRTI and all cause severe LRTI. These will also be presented for each viral etiology identified by the multiplex PCR.

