## 11.11. Interpretation of analyses

For the occurrence of very severe RSV-LRTI among RSV infected infants with a negative RSV exposure status (at screening based on in-stream baseline serological testing) from first vaccination (Day 1) up to the end of the first RSV transmission season, if the upper boundary of the 95% one-sided lower CI of the rate is under 80%, it indicates that the very severe RSV-LRTI rate is less than that of the historic RSV-FI trials [[Kim, 1969](#)].

Comparative analyses will be exploratory and should be interpreted with caution considering that there is no adjustment for multiplicity and that group sizes are small for these comparisons.

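### The 80% FI-RSV benchmark measures a different outcome, in infants vaccinated younger, from the rate tested against it, so meeting the rule shows a rate below 80% and not a rate below the FI-RSV trials

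*Protocol*

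**What the plan says.** Section 11.4 sets up a one-sample test in each RSV vaccine group: "With a one-sided type I error of 0.05, and the assumption of a 10% rate of infection progressing to very severe RSV-LRTI", it states that "5 infections can provide at least 90% statistical power to demonstrate the progression rate from infection to very severe RSV-LRTI is less than 80" percent. The null value is linked to history in the next sentence: "That is less extreme than that observed in the historic FI-RSV vaccine trial where 80% of RSV RTI cases progressed to hospitalization".

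The decision rule follows in 11.4. If at most 1 of 5 infections progresses to very severe RSV-LRTI, the protocol concludes that "the expected progression rate of infection is less than the effect reported in previous FI-RSV trials". Section 11.11 repeats this for an upper confidence bound under 80%: "it indicates that the very severe RSV-LRTI rate is less than that of the historic RSV-FI trials".

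Other sections bear on whether the two rates are comparable:

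- **Outcome.** Table 6 defines RSV-RTI (needs symptoms), very severe RSV-LRTI (low SpO2, inability to feed, or unresponsiveness) and RSV hospitalization (a medical decision to admit) as separate categories.
- **Denominator.** The endpoint in 11.2 is counted among RSV infected infants. Sections 6.6.12.3 and 9.2.2 plan monthly swabs to find asymptomatic infection, and 1.2.4.1 has the IDMC receive "the number of RSV infections (asymptomatic and symptomatic") and the proportion that go on to hospitalization.
- **Age.** Table 1 puts the benchmark trial in the 0-5 month vaccination column. Section 1.2.2.2 says: "Risk of adverse outcome of natural infection following FI-RSV vaccination was more pronounced when the vaccine was administered to younger infants".

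**The concern.** The conclusion compares two rates that differ in what is counted and in whom. History counts admissions among RSV-RTI cases after vaccination at 0-5 months. This trial counts very severe LRTI among infected infants after vaccination at 6-7 months. Two of the differences, age and denominator, make the FI-RSV rate on this trial's own terms lower than 80%. The third, the outcome, probably does too, although the protocol does not say how often an admitted infant meets the very severe definition. No section converts one rate into the other or argues that they are interchangeable.

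The sample size rests on this comparison, and 11.11 gives it as the interpretation of the very severe LRTI endpoint. Section 1.2.1 describes the study as powered to exclude the FI-RSV level of risk, and 1.2.2.1 says it supports moving to infants from 6 weeks of age. Reassurance worded more widely than the data allow would be carried into a younger group.

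**Working it through.** **Inputs.** From 11.4: n = 5 infections per RSV group, null rate 80%, assumed true rate 10%, one-sided alpha 0.05, rule at most 1 of 5. From Table 1, FI-RSV hospitalizations per vaccinee: 4/20 and 16/31 (benchmark trial, 0-5 months), 7/54 (another trial, 6-11 months), and 5/15 (a third trial, in a merged cell that appears to span 6-23 months).

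**1. The protocol's own figures.** P(X ≤ 1) = (1−p)^5 + 5p(1−p)^4.

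- p = 0.80: 0.00032 + 0.00640 = 0.0067. Allowing 2 of 5 would give 0.058, so 1 is the critical value.
- p = 0.10: 0.59049 + 0.32805 = 0.919, which agrees with the stated power of at least 90%.
- The companion rule (at least 3 of 5 shows more than 10%): P(X ≥ 3 | 0.10) = 0.0086. It also reproduces.

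**2. What the rule excludes.** Exact one-sided 95% upper limits with n = 5: 0/5 gives 1 − 0.05^(1/5) = 45.1%; 1/5 gives 65.7%; 2/5 gives 81.1%. At a like-for-like FI-RSV rate of 65%, only 0/5 would reject (power 59.0%). At 45%, not even 0/5 would reject, since 0.55^5 = 0.0503.

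**3. How far 80% could move.** The like-for-like rate is not in the protocol, so these are illustrations.

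- *Denominator.* If 30% of infections are asymptomatic (assumption), 0.80 × 0.70 = 56%. If 50%, 0.80 × 0.50 = 40%.
- *Age.* Scale 80% by a ratio of Table 1 rates, assuming equal infected fractions across trials:
  - 7/54 over 16/31: 0.80 × 0.130/0.516 = 20%
  - 5/15 over 16/31: 0.80 × 0.333/0.516 = 52%
  - 7/54 over 4/20: 0.80 × 0.130/0.200 = 52%
  - 5/15 over 4/20: 0.80 × 0.333/0.200 = 133%, which is impossible as a rate and shows how fragile the scaling is.

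**4. Chance of passing at most 1 of 5 when the true rate equals the FI-RSV-like rate.**

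| Like-for-like rate | P(X ≤ 1 of 5) |
|---|---|
| 80% | 0.7% |
| 56% | 12% |
| 52% | 17% |
| 40% | 34% |
| 20% | 74% |

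**The case against.** Several points on the other side stand.

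- **The endpoint is not judged only against 80%.** A reader might infer that it is, because the relative risks in 11.10 cover RTI and then "The same descriptive analysis will be performed for RSV-associated LRTI and RSV-associated severe LRTI", with no mention of very severe LRTI. But 11.4 has the second rule against the 10% natural-history rate. Section 11.10 also gives incidence with confidence intervals for all Table 6 categories, and infections progressing to hospitalization, in all three pooled groups. Section 9.10.3 adds a progression analysis for the IDMC once each randomised group has at least 5 infections. These are real safeguards, but none supports the two sentences that claim a rate below the FI-RSV trials.
- **The stated 5% error is not breached.** It refers to a true rate of 80%, where the actual error is 0.7%. The larger figures describe a different null value, which had to be assumed.
- **The denominator difference is partly inference.** Section 11.2 says only RSV infected infants, 11.10 tabulates asymptomatic infections separately, and 9.2.2 speaks of asymptomatic RSV-RTI. The protocol does not say how the historical RTI cases were found, and gives no numerator or denominator for the 80%.
- **The age scaling is weak.** Table 1 rates are per vaccinee, not per infection, and come from different trials. The 20% is the lowest result from the rows available. A Table 1 footnote gives an average age of 12 months in season 2, so age at disease may differ less than age at vaccination.
- **The aim is modest.** Section 1.2.4.1 seeks a signal of FI-RSV magnitude with the fewest infants exposed. The endpoint is secondary, and no section makes this rule the go/no-go for the younger group.

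**Conclusion.** The point holds as one of comparability and wording. The calculation is correct for 80%. What meeting the rule establishes is a rate of very severe RSV-LRTI below 80%, or more precisely below 65.7% (1/5) or 45.1% (0/5). It does not establish a rate below that of the FI-RSV trials unless the FI-RSV rate on the same outcome, denominator and age exceeds those limits. The protocol does not give that rate, and its own text on age and on asymptomatic infection points to one lower than 80%.

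The size is uncertain. Pass probabilities of 12% and 34% rest on assumed asymptomatic shares of 30% and 50%; the 17% and 74% rest on Table 1 scaling with equal infected fractions. A reader might take 74% as the expected chance of false reassurance, but the documents do not support that: it comes from one choice of rows, and others give 17%. The mismatch itself depends on none of these assumptions, because outcome and age at vaccination differ on the face of the protocol.

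**What to change.** 1. **Narrow the conclusion (11.4 and 11.11).** Replace the statements that "the expected progression rate of infection is less than the effect reported in previous FI-RSV trials" and that "it indicates that the very severe RSV-LRTI rate is less than that of the historic RSV-FI trials" by a statement that the rate is below 80%. Say beside it that 80% is a hospitalization rate among RSV-RTI cases in infants vaccinated at 0-5 months. Report the exact one-sided 95% upper limit, with the 6-11 month figures of Table 1 as context. Reconcile the entry there printed as 13.7%, since 7/54 = 13.0%.
2. **Add control contrasts (11.10).** Include very severe RSV-LRTI and RSV hospitalization among the exploratory contrasts of each RSV group with the randomised control, by exact methods. A statistical analysis plan not seen here may already do so; the protocol list should then match.
3. **Add a supportive comparison.** Show hospitalization among symptomatic RSV-RTI cases beside the 80%, descriptively.

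The third item should not replace the formal rule. Its denominator is smaller: with 3 symptomatic cases only 0/3 passes (power at 10%: 0.9^3 = 73%), and with 2 only 0/2 (0.9^2 = 81%), both short of 90%. It also depends on local admission practice, because 1.2.4.1 leaves hospitalization criteria to the attending clinician, and it keeps the age difference.

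The cost is a narrower claim and a few table rows from data already collected. Sample size and study procedures are unchanged.
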